**Reference Codes:**

**UCL Sponsor Code: 17/0126**

**Start Date of study: 1/3/17**

**Project Duration: 5 years**

**Abbreviations:** Parkinson's disease – PD; idiopathic Parkinson's disease – IPD; cerebrospinal fluid (CSF); PD patients with detectable mitochondrial dysfunction – mito-PD; PD patients without detectable mitochondrial dysfunction – amito-PD;

## PROTOCOL VERSIONS

Version Stage	Versions No	Version Date	Protocol updated & finalised by;	Appendix No detail the reason(s) for the protocol update
Previous	1.0	12/4/17	[name]	-
Current	1.1	04/10/2017	[name]	Added RNA collection and processing

## **2. Summary**

**Title:** **Systems Medicine of Mitochondrial and biochemical Parkinson's Disease and other related movement disorders**

**Short title:** **SysMedPD**

**Objectives:** Stratification of PD patients based on biochemical markers to develop novel neuroprotective therapeutic approaches.

**Type of trial:** Basic science study with human subjects

**Trial design and methods:** Genetic analysis, biological material sampling, biochemical assays, cell line generation.

**Trial duration per participant:** 24 months (up to 3 study visits in 2 years)

**Estimated total trial duration:** 5 years (includes 2 years for additional data analysis)

**Planned trial sites:** Multi-site (Royal Free Hospital Trust and National Hospital for Neurology and Neurosurgery, UCLH NHS Trust)

**Total no. participants planned:** 160

**Main inclusion/exclusion criteria:**

**Inclusion** – Affected by Parkinson's disease (PD) or a related disorder or unaffected by PD or related disorder for control cohort

**Exclusion** – Participants with dementia, under 18 years of age.

**Statistical methodology and analysis:**

Screening for genetic mutations associated with PD, biochemical analysis of biosamples (blood components and tissue) by a variety of methods (Seahorse, flow cytometry etc) to stratify patients into groups with and without dysfunction in the studied biochemical process (e.g. mitochondrial dysfunction). Statistical analysis will include univariate and multivariate statistics such as principal component analysis, linear mixed models, partial least squares regression and ANOVA simultaneous component analysis.

### **3. Introduction**

**3.1 Background:** Parkinson's disease (PD) is a progressive neurological disorder that is increasingly prevalent with age, with the incidence rising from approximately 4 people per 10,000 in their forties to 2 in 100 over the age of eighty. Besides motor symptoms, such as tremor, rigidity, bradykinesia, and postural instability, PD patients often experience a variety of non-motor symptoms, such as fatigue, depression, sleep disturbance, and dementia.

Although symptomatic treatments exist to partially compensate for motor dysfunction, no neuroprotective treatment has yet been established to slow PD progression, which inevitably renders patients incapable of living independently. Compared to age- and sex-matched controls, PD patients are about 5 times more likely to require nursing home care and this care costs about 5 times more than average nursing home care. This, combined with the European demographic shift toward an increasingly larger fraction of aged individuals, creates a social and economic challenge to develop new medications to slow the progression of PD.

Our understanding of the aetiopathogenesis of PD has rapidly developed in the past two decades, but this has not yet translated into any clinically established neuroprotective treatment that slows disease progression. There is a growing consensus that the failure of previous efforts is mainly due to the aetiopathogenic diversity of PD and the estrangement of existing preclinical models from clinical PD. For example, it is known that mutations in mitochondrial genes can cause monogenic PD and biochemical evidence indicates that in a proportion of cases, idiopathic PD is associated with detectable mitochondrial dysfunction.

Therefore, our focus is on monogenic forms of PD that involve mitochondrial abnormalities as a primary (e.g., Parkin, PINK1), or secondary (e.g., LRRK2, GBA1) phenomenon, in order to extrapolate to idiopathic PD (IPD) patients with and without mitochondrial dysfunction (Mito-IPD and Amito-IPD, respectively). Biochemical pathways focussing on, but not restricted to mitochondrial function, will be assessed using a variety of techniques including biochemical assays on blood, urine, CSF and tissue samples. We will explore both the relevance and measurement of specific biochemical pathways in Parkinson's and related disorders

The main overall objective is to stratify PD patients based on dysfunction in biochemical pathways related to PD. This will aid in developing new candidate neuroprotection compounds to slow the progression of neurodegeneration.

**3.2 Ethical considerations:** The primary ethical considerations here are accurate informed consent, data security and potential adverse events related to study procedures, which will be monitored through the study.

**3.3 Risks/benefits:** This is a basic science study involving procedures to human participants. The primary risks of this study will be:

(1) Potential adverse events related to study procedures which will be mitigated by careful monitoring throughout the study

(2) Causing increased anxiety about risk to family members of developing PD, which will be mitigated (i.) the provision of NHS-based genetic counselling and support where needed and (ii.) patient and public engagement through education about the results and implications of research as the study progresses.

#### **4. Objectives**

To identify participants with known monogenic forms of PD and related disorders (PINK1, parkin, GBA, LRRK2) for biochemical assessment of blood, urine, CSF and tissue samples to identify defects in specific biological pathways (e.g. mitochondrial dysfunction). The most informative of these assays will then be applied to participants without genetic mutations (IPD) to stratify them based on dysfunction in these biochemical pathways.

#### **5. Study design**

It is planned that 160 participants will be recruited to the study (comprising 100 with idiopathic Parkinson's disease, 30 with genetic forms of Parkinson's disease and 30 healthy control subjects). This is based upon power calculations conducted by the University of Luxembourg (who constructed the initial EU study proposal).

Participants will be asked to take part in up to 3 visits, one at baseline where a full assessment including clinical assessment and biosamples donation will take place, an optional visit for skin biopsy and/or CSF sampling and one further visit 1-2 years post entry into the study for repeat assessment and biosamples collection for participants with PD only. Data and samples will be collected in a standardised format and, following site based subject anonymization, will be entered onto a secure web-based database. To develop a patient registry, subjects can provide consent for permission to be contacted if further/additional research projects were to become available.

All participants must consent to the core protocol of clinical assessment and blood and urine donation. CSF and skin biopsy consent is highly desirable but optional. Skin biopsies will be requested from some study participants including unselected PD patients, healthy controls and PD patients with defined genetic and/or biochemical phenotypes. If participants are identified as being in particular cohorts of interest post baseline assessment/sampling analysis (e.g. the mito-PD or amito-PD groups) then cell lines generated from skin biopsies from these participants will be used to create advanced cell models, such as induced pluripotent stem cells and dopaminergic neurons for further biochemical analysis and validation of initial findings. All monogenic PD participant skin biopsy samples will be used to generate such models.

Patients will be asked if they want to be informed of the availability of NHS genetic or biochemical tests which emerge as a result of this research. Participants will not be made aware of the cohort they fall into as currently this will not change their medical care, however consent will be sort to re-contact patients based on the results of this study if these results suggest they will be eligible for novel therapies for PD or would be eligible to take part in future studies or clinical trials related to Parkinson's disease. Control subjects will be asked to

complete baseline clinical assessments and donate biosamples but will not be asked to return for any further study visits.

**Table 1 – SysMedPD overview**

	Visit 1	Visit 2 (optional)	Visit 3 - 24-48 months (for those affected by PD only)
Study personnel administered			
Informed consent	X		X
Demographic information	X		X
Parkinson’s disease history	X		X
Past medical history	X		X
Medication history	X		X
Family history	X		X
Environmental exposure	X		X
MDS-UPDRS clinician	X		X
Tremor Spirals	X		X
Handwriting	X		X
MoCA	X		X
Patient completed			
MDS-UPDRS patient	X		X
PDSS2	X		X
ESS	X		X
HADS	X		X
WHO QoL (BREF)	X		X
Biomarkers			
Blood for DNA	X		X
Blood for RNA	X		X
Blood PBL/LCL	X		X
Blood for Serum	X		X
Blood for Plasma	X		X
Blood for cellular components	X		X
Urine	X		X
Optional Assessments			
Video assessment	X		X
CSF		X	
Skin biopsy		X	

**5.1 Inclusion/exclusion criteria:**

Inclusion 1. Diagnosed with PD, or a related condition (e.g. Parkinson’s plus, dystonia, tremor) or healthy control participant

2. Age 18 years or over

Exclusion 1. Lack of capacity to consent to participate in the project

#### Additional lumbar puncture and skin biopsy exclusion criteria

1. Anticoagulants such as warfarin
2. Known coagulation abnormalities – known coagulopathy
3. Lumbar spinal surgery within 6 months prior to assessment, or any lumbar spinal surgery that interferes with anatomy of the inter-vertebral space (LP).
4. History of chronic or repeat CSF leakage following previous lumbar puncture or history of spontaneous or traumatic intracranial hypotension (LP)
5. Active infectious process
6. Allergy/hypersensitivity to local anaesthetic

#### **5.2 Recruitment:** Participants will be identified in the following ways:

a) By the study team from existing biobank studies that UCL is collaborating on, where the patient has consented to be re-contacted.

b) By the clinical care team/ their treating physicians through movement disorder and neurology clinics in the course of normal clinical care.

c) Participants may contact the study team directly, for example after reading adverts on PD charity websites, in this instance participants will need to complete and return a 'permission to contact form' to the study team.

d) Participants friends/spouses who plan to attend study/clinic visits with the participant may also be approached to join the study as control subjects. This will be done by the study team. During study visits participants can be given permission to contact forms and information leaflets to give to friends/spouses who they feel may want to enrol in the study as a control subject

Participants will be provided with written information on the study before they participate, either via email or regular post. The primary research clinics will be based at the Royal Free London Foundation Trust and UCLH. Participants will be approached by their caregiver in the course of normal clinical care or by caregivers holding registries of patients who have agreed to be contacted for research purposes.

**5.3 Consent:** Written Informed consent will be obtained by individuals trained in GCP; and in consent procedures specific to this study. The consent process will be guided by a standard operating procedure (SOP). Standardised patient information sheets (PIS) and consent forms will be used. Participants can withdraw from the study any time without giving reasons.

**5.4 Study assessments:** Potential participants will sign an informed consent form prior to any study-related procedures, which will involve agreement to:

1. A brief structured clinical interview (30 mins) that will obtain details of patient demographics, PD history, past medical history, medication history, family history and environmental exposures (based on MERQ-PD questionnaire). This will also include reviewing participants NHS records.

2. A structured clinical examination (15mins) consisting of the following standardised examinations:

- a. MDS-UPDRS
- b. Montreal Cognitive Assessment (MoCA)
- c. Handwriting and spiral drawing assessment

Examinations may be videotaped for confidential research analysis, for example validation of clinical diagnosis, and rating scale assessment by another member of the research team

3. Standardised validated patient self-completion questionnaires (20mins – can be done at home) including Epworth sleepiness scale (ESS), Parkinson's disease sleep scale 2 (PDSS2), WHO Quality of Life scale short version (WHOQol – BREF), Hospital Anxiety and Depression scale (HADS) and Scales for Outcomes in Parkinson's disease - Autonomic (SCOPA-AUT).

**5.5 Biosamples:** All participants will be invited to donate blood, urine and CSF at the initial study visit. All samples will be taken and stored using a standardised protocols. Participants will be asked to fast for 10-12 hours where possible before biosamples are taken. All samples will be labelled with a unique study identifier.

a. Blood – each participant will be invited to donated up to 100mls of blood for DNA, analysis, **RNA analysis**, storage of immortalised peripheral blood lymphocytes (PBLs) (see below), plasma and serum samples, and extraction of blood cells (red blood cells, white blood cells and platelets) for biochemical assessment (such as mitochondrial function).

b. Urine - a mid-stream urine sample will be collected from each participant

c. CSF – Consent to CSF sampling is highly desirable but optional. For participants who agree to donate CSF a lumbar puncture will be performed. An information sheet on lumbar puncture will be provided to the participant. Local protocols should include the ability to perform a blood patch if necessary for persisting low- pressure headache. Lumbar punctures for CSF collection are performed using a small calibre needle in either a sitting or lateral decubitus position. CSF is obtained via gravity flow into polypropylene tubes. The first 0.5-1ml will be discarded due to potential contamination with blood. 5-10ml of CSF will then be collected for storage. Participants who are having a lumbar puncture as part of their routine clinical care, treatment or as a research procedure will be asked if they will donate surplus CSF for research purposes.

d. Skin biopsy – Skin biopsy consent is highly desirable but optional. A proportion of participants will be asked to donate a skin biopsy. Skin biopsies will yield both skin and underlying fat samples. The area for biopsy will be scrubbed with 70% isopropyl alcohol and local anaesthetic will be instilled prior to removal of a skin and underlying fat sample by sterile punch biopsy instrument (4- 6mm depending on the participant's build). The skin will be closed with steristrips in most cases. Occasionally it is anticipated that a single stitch will be required and if this is the case the participant will be instructed to attend their GP surgery to

have the stitch removed by the practice nurse in one week's time. The patient will be given an information sheet on post skin biopsy management. Skin punch will be carried out by clinically qualified personnel at all centres or where appropriate, at the participant's home. The skin and fat sample will be transferred to the laboratory for further processing. Here fibroblast (from skin) and adipose stem cell (from fat) lines will be established using standard methods.

**5.6 Controls:** Individuals who are not blood relatives of the patient are eligible to participate as an unaffected control. Typically this will be the spouse or a close friend of the affected SysMedPD patient, but not their son, daughter or sibling. Permission to contact forms and patient information leaflets will be given to participants in the study to pass onto friends/spouses who would be eligible to enrol as control subjects. Alternatively, at study/clinic visits where a participant is accompanied by a friend/spouse who would be eligible to enrol as an unaffected control, the study team will invite the individual to take copies of the participant information sheet and consent form, as well as a 'permission to contact form'. If they would like to enrol then they can return the permission to contact form to the study team. Finally unaffected controls can contact the study team directly, for example after reading adverts on PD charity websites. In this instance they would need to complete and return a 'permission to contact form' to the study team. Unaffected individuals can participate by completing study questionnaires/assessment and donating blood samples, and if possible CSF collection and skin biopsy. They will not be required to undergo a second follow up visit.

## **6. Sample analysis/processing**

**6.1 Screening for genes related to PD:** Blood samples will be sent to UCL Institute of Neurology Neurogenetics Lab for DNA extraction and storage to be carried out in accordance with the analytical plan agreed with the Chief Investigator. The Neurogenetics Laboratory will process, store and dispose of blood samples in accordance with all applicable legal and regulatory requirements, including the Human Tissue Act 2004 and any thereto. Genetic analysis may include large scale sequence, copy number and single nucleotide variant analysis. **Similarly RNA will be extracted from whole blood and analysed using RNA sequencing (RNAseq).**

**6.2 ECACC:** Consent will also be sought for a coded blood to be sent to the European Collection of Cell Cultures - Porton Down (ECACC) for storage of peripheral blood lymphocytes (PBLs) and ultimately the preparation of immortalised cell lines for affected individuals only. No personal identifiers will be sent with this sample. However to enable the cell line to be of optimal use to the research community, strictly limited details of the subject will accompany the sample, specifically sex, race and year of birth. No further personal identifying details will be released to ECACC. The code linking the samples will be kept strictly confidential by the research group, on the encrypted NHS computer system in a folder whose access restricted by the study PI. Subjects can request withdrawal of their samples from ECACC at any point. The European Collection of Cell Cultures will process, store and dispose of blood samples in accordance with all applicable legal and regulatory requirements, including the Human Tissue Act 2004 and any amendments thereto. The custodian and Human Tissue Act Designated

Individual for ECACC is [name] (MSc C.Biol MSB) - Head of Culture Collections for Public Health England (PHE) (contact details: email: [[contact]](mailto:[contact]); direct [contact])

**6.3 Assessment of biochemical pathways:** This will involve analysis of plasma, serum, urine, CSF, blood cellular components and tissue taken from participants. If participants have already donated samples to another approved study lead by the principle investigators or their collaborators (such as the Clinical Neurological Disorders DNA and Serum Research Bank - CANDAS), and there is consent to use samples in collaborating projects, then these samples will be requested from the CANDAS study to reduce patient burden. Various pathways thought to be involved in PD (such as mitochondrial dysfunction) will be investigated using a range of laboratory techniques such as flow cytometry, seahorse extracellular flux analysis and metabolomic analysis. The aim is to use these pathways to stratify participants into cohorts with and without dysfunction in the studied biochemical pathway.

**6.4 Collaboration – incoming data/samples:** The research group may analyse anonymous samples provided by collaborators where an MTA is in place and where samples have been collected with appropriate local ethical approval.

**6.5 Collaboration – outgoing samples:** The research group will collaborate with national and international groups engaged in neurology research, principally in the EU for analysis as above. This project is part of a large European wide project involving multiple sites across Europe and is being funded primarily by an EU ‘Horizon 2020’ grant. This will involve sharing anonymised samples for specific analysis which will be carried out at other sites, e.g. “metabolomics” in the Netherlands. Pseudo-anonymised data will accompany the samples. Appropriate material transfer agreements (MTAs) will be used. Participants will be asked whether they consent to sharing of their pseudo-anonymized data.

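### Banked samples may stand in for study samples in the biochemical assessment, more likely in patients than in controls, and the SAP does not account for sample source

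*Protocol*

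**What the plan says.** Protocol Section 6.3, which covers the biochemical pathway assays, sets two conditions for using earlier material. The first is prior donation: "If participants have already donated samples to another approved study lead by the principle investigators or their collaborators". The second is permission: "and there is consent to use samples in collaborating projects". If both hold, "then these samples will be requested from the CANDAS study to reduce patient burden". CANDAS is given as an example, and its full name describes a DNA and serum bank. The section lists fluids, blood cells and tissue as materials, and flow cytometry, Seahorse and metabolomics as techniques. It does not say which of these may use banked material.

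Protocol Section 5 says: "All participants must consent to the core protocol of clinical assessment and blood and urine donation". Table 1 schedules these samples at Visit 1 and exempts no one with banked samples.

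Section 5.5 calls for standardised taking and storage, and adds: "Participants will be asked to fast for 10-12 hours where possible before biosamples are taken". It has no rule for samples taken before the study.

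On recruitment, Section 5.2 lists as route (a): "By the study team from existing biobank studies that UCL is collaborating on, where the patient has consented to be re-contacted". For controls, Section 5.6 says: "Typically this will be the spouse or a close friend of the affected SysMedPD patient". The other control route is self-referral.

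The SAP (Statistical analysis, item 1) builds the signature by comparing monogenic PD with controls matched on age and sex. Item 2 uses it to stratify idiopathic PD, with a first cut-off of 1 SD from the control mean. Neither item mentions sample source, storage time or fasting.

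**The concern.** Samples from an earlier study have been stored longer and may have been collected under another procedure. If that moves an assay, and if banked samples are commoner among patients, sample source is confounded with disease status in the one comparison that decides which assays count as informative. An assay could then be selected because it responds to storage or handling.

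The error would not stop there. The selected assays go on to grade the idiopathic patients against the control mean, and that grading guides whose skin biopsies are turned into advanced cell models. If sample source is not recorded at the time, it may be hard to recover later.

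**Working it through.** **Step 1. Is there a path from sample source to group?** The plan gives no figure to reproduce here, so the first check is textual.

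| Question | Patients | Controls |
|---|---|---|
| Is a biobank recruitment route listed? | Yes, Section 5.2 route (a), worded for patients | None listed (Sections 5.2 and 5.6: spouse, friend, self-referral) |
| May earlier samples be requested? | Yes, Section 6.3 | Yes if they donated before; Section 6.3 refers to participants generally |
| Are blood and urine required in this study? | Yes, Section 5 | Yes, Section 5 |
| Are banked samples covered by Section 5.5? | Not stated | Not stated |
| Is source handled in the SAP? | No | No |

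Patient burden falls only if some new collection is skipped or reduced, so Section 6.3 points to some substitution. Section 5 and Table 1 point the other way. Both cannot apply in full to blood and urine.

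**Step 2. How large could the effect be?** Inputs from the documents are 30 monogenic patients, 30 controls and 100 idiopathic patients (Section 5), and the Wilcoxon-Mann-Whitney test at 0.05 (SAP, Sample size). Assumed inputs are two-sided testing, normal data, no true disease effect, a share f of patient samples banked, no control samples banked, and an assay shift of s SD in banked samples. The documents give neither f nor s.

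The false mean difference is f × s. For example, 0.5 × 1 = 0.5 SD, numerically equal to the effect size of 0.5 used in the SAP's power statement.

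For the test itself, the probability that a patient value exceeds a control value is

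P = 0.5 + f × (Φ(s/√2) − 0.5),

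with null standard error √[(n1 + n2 + 1)/(12 × n1 × n2)]. For 30 v 30 this is √(61/10,800) = 0.0752.

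- f = 0.5, s = 0.5: P = 0.5 + 0.5 × (0.638 − 0.5) = 0.569; z = 0.069/0.0752 = 0.92; rejection rate Φ(0.92 − 1.96) + Φ(−0.92 − 1.96) ≈ 0.15.
- f = 0.5, s = 1: P = 0.5 + 0.5 × (0.760 − 0.5) = 0.630; z = 0.130/0.0752 = 1.73; rejection rate ≈ 0.41.

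Simulation of the same model (8,000 runs per cell) agrees to within about 2 points:

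| Comparison | Share banked in patients | s = 0.25 | s = 0.5 | s = 1.0 |
|---|---|---|---|---|
| 30 v 30 | one quarter (8 of 30) | 0.05 | 0.07 | 0.14 |
| 30 v 30 | one half | 0.08 | 0.14 | 0.40 |
| 30 v 30 | all | 0.15 | 0.46 | 0.96 |
| 100 v 30 | one half | 0.09 | 0.20 | 0.59 |

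**Step 3. Is imbalance the cause?** With half banked in both groups of 30 and s = 0.5, the simulated rate is 0.04, which is nominal. The harm comes from unequal use by group, not from banked samples as such.

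**Step 4. The 1-SD cut-off.** An unaffected sample crosses the cut-off on the side of the shift with probability Φ(−1 + s). This is 16% with no shift, and 23%, 31% and 50% for s = 0.25, 0.5 and 1.0. It assumes that the control mean and SD come from unshifted samples.

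**The case against.** The strongest reply is that the documents show less than the risk suggests.

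- **Replacement.** A reader might infer that banked samples will replace fresh ones. The text says only that they will be requested, under two conditions, and Section 5 still requires new blood and urine. The stated aim of reducing burden makes some substitution the natural reading, but its extent is unknown.
- **All assays.** A reader might extend the point to every assay. The only named bank holds DNA and serum, and nothing shows that Seahorse or flow cytometry would use banked material. The supported concern is stored fluids, mainly serum.
- **Patients only.** A reader might infer that no control will have banked samples. The routes lean that way, but route (a) is not given priority, no share is stated, and a control who donated earlier is not excluded. It is also an inference that known mutation carriers are more often banked.
- **Handling.** CANDAS procedures are not described. The bank is at UCL under a co-principal investigator of this study (Section 9.2), so similar handling cannot be ruled out. Fasting is requested only where possible for study samples too, so variable fasting is not specific to banked material.
- **Downstream check.** Section 5 plans cell models to validate initial findings. These might expose a false signature, but only after the signature has guided the choice of patients.

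These replies limit how strongly the point can be put. None supplies a rule on which assays may use banked material, or any handling of source in the analysis.

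**Conclusion.** The concern holds as a possible, uncontrolled confounding path, not as a demonstrated bias. Section 6.3 admits banked material to the biochemical assessment, the listed routes make its use more likely in patients, and neither document controls for source.

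The size is conditional. At a quarter banked with a shift of 0.25 to 0.5 SD, or half banked with 0.25 SD, the false-positive rate is about 5% to 8%, which is little harm. At half banked it is 14% for a 0.5 SD shift and 40% for a 1 SD shift. These figures assume no banked controls and describe a single univariate test, whereas the SAP also names multivariate selection methods. The 40% figure should not be read as an expected error rate, because nothing in the documents supports that particular share or shift. The point merits a change because the remedy for blood and urine is cheap.

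**What to change.** 1. Reconcile Protocol Sections 5 and 6.3: state whether a participant with banked samples still gives study blood and urine, and which assays may use banked material.
2. For blood- and urine-based assays that build or apply the signature, use the Visit 1 samples that Section 5 already requires, in patients and controls alike.
3. Where banked material is still used, for example CSF or tissue, record its source, storage time and fasting hours. Include source as a covariate, and repeat the assay selection on samples collected in this study only. Put the covariate and the repeat analysis in the SAP.

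Limiting all substitution to DNA might look simpler, but it would not be cheap: recollecting CSF or tissue needs a lumbar puncture or biopsy, both optional here. Item 3 is meant for those materials.

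**Cost.** Item 2 adds no draw beyond what Section 5 and Table 1 already specify, but the stated burden reduction is lost for blood and urine. Item 3 adds a few data fields and a little analysis. If nearly all banked samples are in patients, the covariate will be estimated imprecisely, so the repeat on study samples is the more informative check.
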